#### **4.7. Subsequent Anti-myeloma Therapies**

The total number of subjects who received subsequent anti-myeloma therapy for multiple myeloma will be reported for the ITT analysis set in each treatment group. A summary of subsequent anti-myeloma therapy will be presented by therapeutic class, pharmacologic class and preferred term.

### **5. EFFICACY**

#### **5.1. Analysis Specifications**

##### **5.1.1. Level of Significance**

All hypotheses testing will be conducted at a 2-sided level of significance of 0.05. When required, 95% confidence intervals will be constructed.

The primary hypothesis is to be tested at the 0.05 significance level. If the primary endpoint of PFS is statistically significant at the primary analysis, the following secondary endpoints ordered below will be sequentially tested, each with an overall two-sided alpha of 0.05, by utilizing a hierarchical testing approach as proposed by Tang and Geller (1999) that strongly controls Type I error rate:

- ORR
- PFS2
- OS

If the null hypothesis for any of the endpoints fails to be rejected at the primary analysis time point, then any of the subsequent endpoint(s) listed above will not be tested until the next analysis timepoint, if applicable. If the null hypothesis for an endpoint is rejected at a analysis time point, it will remain being rejected and will not be re-tested at the next analysis timepoint, if any. The significance level for each of the above secondary endpoints will be determined by the alpha-spending function specific to the endpoint. The ORR will only be tested at the primary analysis time point with a 2-sided level of significance of 0.05. For PFS2, and OS, alpha spending at the primary analysis time point and the final analysis point will be determined by a linear alpha spending function based on the observed number of the events at the time, i.e., the cumulative alpha to be spent will be the total alpha (0.05) multiplied by the proportion of the observed number of the events out of the total expected number of the events. For example, if 59% targeted PFS2 events are observed at the primary analysis, the corresponding alpha level will be 0.0295(2-sided)). A total of 134 PFS2 events and a total 107 OS events are expected at the final analysis.

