### **1.3. Statistical Hypotheses for Trial Objectives**

The primary efficacy endpoint of this study is PFS. The null hypothesis is that there is no difference in PFS between daratumumab and active monitoring in subjects with high risk SMM.

The null hypotheses ( $H_0$ ) of no difference between the two groups (daratumumab SC and active monitoring) will also be evaluated for the following secondary endpoints:

- ORR
- PFS2
- OS

These secondary hypotheses are to be tested in a sequential order as specified above. The details of the testing procedure are specified in Section [5.1.1](#).

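### SAP 5.1.1 does not secure the strong type I error control it claims: after a failed ORR test, PFS2 and OS are deferred to the final analysis instead of being closed

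*SAP*

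**What the plan says.** The rules are in SAP 5.1.1 (Level of Significance). Protocol 11.3.2 leaves the hierarchy to the SAP.

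- **Gate on PFS.** "If the primary endpoint of PFS is statistically significant at the primary analysis, the following secondary endpoints ordered below will be sequentially tested". The order is ORR, PFS2, OS, each with an overall two-sided alpha of 0.05.
- **Method.** The SAP cites the Tang-Geller hierarchical approach and describes it as one "that strongly controls Type I error rate". SAP 1.3 adds: "These secondary hypotheses are to be tested in a sequential order as specified above".
- **After a failure at the primary analysis.** For the endpoints lower in the order, "then any of the subsequent endpoint(s) listed above will not be tested until the next analysis timepoint, if applicable".
- **ORR.** "The ORR will only be tested at the primary analysis time point with a 2-sided level of significance of 0.05".
- **PFS2 and OS.** Each has two looks, at the primary and the final analysis, with linear spending: "the cumulative alpha to be spent will be the total alpha (0.05) multiplied by the proportion of the observed number of the events". The denominator is the count planned for the final analysis: 134 for PFS2 and 107 for OS.

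**The concern.** A fixed-sequence procedure holds the family-wise error rate only if an endpoint is tested after every endpoint ahead of it has been rejected. The deferral sentence says when later endpoints may next be tested, but not on what condition.

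For ORR the omission creates a direct conflict. ORR has no second look, so a failed ORR stays failed. A closed hierarchy would end there. The sentence instead moves PFS2 and OS to the final analysis.

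For PFS2 to OS, the sentence leaves open whether OS may be formally tested at the final analysis when PFS2 has been rejected at neither look. At stake is a confirmatory claim on PFS2 or OS that the stated error control does not cover, and a disagreement about that claim once the final data are known.

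**Working it through.** **Inputs.** Two-sided alpha 0.05, linear spending, and totals of 134 PFS2 and 107 OS events (SAP 5.1.1). At the primary analysis, 81 PFS2 and 64 OS events are expected, and the assumed PFS2 hazard ratio is 0.75 (protocol 11.2). There are 180 subjects per arm (SAP 1.4). Phase 2 response rates run from 37.5% to 56.1% across three IV schedules (protocol 3.2, Table 4). The correlations between endpoints are not in the documents. They are assumed: 0 to 0.9 between PFS2 and OS, and 0 or 0.3 between ORR and the other two. PFS is taken as significant, so the secondary family is open.

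**1. The plan's own figure.** 0.05 × 0.59 = 0.0295, as the SAP states.

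**2. Levels at the planned event counts.**
- PFS2 at the primary analysis: 0.05 × 81/134 = 0.0302 (critical value 2.167).
- OS at the primary analysis: 0.05 × 64/107 = 0.0299 (critical value 2.171).
- The final critical values are solved so that the chance of crossing at either look is 0.05 under the null, with correlation between looks equal to the square root of the event fraction. This gives 2.152 for PFS2 (nominal 0.0314) and 2.151 for OS (nominal 0.0315).

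**3. ORR null, with PFS2 tested at the final analysis despite the ORR failure.** The first error can come from ORR itself (0.05). Otherwise it comes from PFS2 at its final look:

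0.05 + 0.95 × 0.0314 = 0.080

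This is the independence case with OS still gated on PFS2. Simulation with 2,000,000 runs per setting gives 0.079 to 0.080 across the correlations.

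**4. All three null, with OS also opened at the final analysis regardless of PFS2.** Under independence:

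0.05 + 0.95 × [1 − (1 − 0.0314)(1 − 0.0315)] = 0.109

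The simulated range is 0.092 to 0.109.

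**5. ORR truly different, PFS2 and OS null.**
- If OS follows only a rejected PFS2, the error is 0.050.
- If OS is tested at the final analysis whatever PFS2 shows, independence gives 0.05 + 0.95 × 0.0315 = 0.080. The simulated range is 0.062 (correlation 0.9) to 0.080 (correlation 0).

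**6. PFS2 truly effective at hazard ratio 0.75, OS null, ORR rejected.** PFS2 is rejected at the primary analysis with probability 0.19. On the literal reading OS then gets both looks; otherwise it gets the final look only. Under independence:

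0.19 × 0.05 + 0.81 × 0.0315 = 0.035

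The simulated range is 0.035 to 0.041. It cannot exceed 0.05, because OS is capped by its own spending.

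**7. How likely is an ORR failure?** For response rates of 37.5% to 56.1% on daratumumab against an assumed 1% to 10% on monitoring, power at 180 per arm is above 0.999. For an assumed 20% against 10% it is 0.76.

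**8. With an explicit gate.** If an endpoint is tested only after every earlier one has been rejected, and a failed ORR ends the hierarchy, simulated family-wise error is 0.050 in every setting (0.0497 to 0.0503).

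**The case against.** The strongest reply is that the sentence prohibits and does not permit. The word until sets an earliest time and does not waive the order. The same paragraph prescribes sequential testing by a named closed procedure, and SAP 1.3 repeats the order. PFS2 has its own second look, and carrying a failed endpoint to its own next look is legitimate in a group-sequential hierarchy. Applied at the final analysis, the order means PFS2 is retested and OS follows only if PFS2 is rejected, which keeps 5.0%. For ORR, the words if applicable could be read as recognising that it has no next look. Nor does a failed PFS reopen anything, because the secondary tests require PFS to be significant at the primary analysis.

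Most of this stands for PFS2 to OS, where the fault is ambiguity. It does not settle ORR. There the next timepoint exists for PFS2 and OS, so if applicable does not clearly close them, and only the method citation suggests that they stay closed.

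A reader might infer that error control is lost outright. The documents do not support that, because the sequential reading is available and holds 5%. A reader might also note that PFS2 is rejected at the primary analysis only about 19% of the time at the protocol's hazard ratio, and conclude that inflation is the usual outcome. That mixes two scenarios. The 19% assumes PFS2 works, and in that case even the literal reading gives 3.5% to 4.1%. The 6.2% to 8.0% needs PFS2 to be null.

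**Conclusion.** The point holds as a defect of wording with a type I error consequence. In the ORR branch the rule is wrong as written: it defers endpoints that a closed hierarchy would shut, and family-wise error is then about 8% with ORR and PFS2 null, or about 9% to 11% if OS is also opened with all three null. The practical likelihood is low, because ORR should be rejected with near certainty if response resembles phase 2 and is uncommon on monitoring. The documents give no monitoring response rate.

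In the PFS2-to-OS branch the text allows two readings: 5.0% on the sequential one, and about 6.2% to 8.0% on the literal one if both endpoints are null. Strong control must hold under every combination of true and false null hypotheses, so a small chance of the adverse case does not rescue the statement in the SAP. The sizes rest on the planned event counts and the assumed correlations.

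**What to change.** Replace the deferral sentence in SAP 5.1.1 with:

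> At any analysis an endpoint is formally tested only if every endpoint ahead of it in the order has been rejected at that or an earlier analysis. If ORR is not rejected at the primary analysis, PFS2 and OS are not formally tested. At the final analysis OS is tested only if PFS2 has been rejected at the primary or final analysis.

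This is a short text change. It alters no boundary, event count, sample size or data collection, and it removes only claims that strong control never allowed. It should be settled before the final PFS2 and OS data are seen.

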Assessment of disease response will be conducted in accordance with the IMWG response criteria (Table 8) using a validated computer algorithm. Disease progression will be assessed using the IMWG diagnostic criteria for MM using a computer algorithm. Cases for which progression is based on FLC criteria only, progression will be determined based on modified FLC criteria combining IMWG progression criteria with IMWG FLC ratio criteria (Section 9.2.2). Progression evaluations for the primary endpoint/final analysis will be based on IRC review, in a blinded fashion, to objectively and consistently implement the IMWG diagnostic criteria for MM (Section 9.2.2). Evaluation of disease progression by IRC and validated computerized algorithm will be discontinued once the number of planned PFS events for the primary analysis is achieved. Per protocol Amendment 6, following the primary analysis, disease evaluations will be conducted locally and disease progression will be assessed by the study investigator according to IMWG criteria.

Safety evaluations will include adverse event monitoring, physical examinations, SC injection site evaluations, clinical laboratory parameters (hematology and chemistry), and Eastern Cooperative Oncology Group (ECOG) performance status. Blood samples will be drawn for assessment of PK and biomarker parameters. All study evaluations will be conducted according to the Time and

[figure not shown]
Events Schedules ([Table 1](#) and [Table 2](#)). An Independent Data Monitoring Committee (IDMC) will review safety data at regular intervals during the study.

Three data cutoff time points are planned:

- The first is for an interim analysis for futility when approximately 60% of the planned PFS events (99) have occurred. This is expected to occur approximately 8 months after the last subject has been randomized. All available data at the time of this data cutoff will be included in the interim analysis.
- The second is for the primary analysis and will occur when approximately 165 PFS events have occurred. This analysis is expected to occur approximately 2 years after the last subject is randomized. All available data at the time of this data cutoff will be included in the Clinical Study Report.
- A third will occur at the end of the study. The data collected will be reported as an addendum to the Clinical Study Report.

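### The linear alpha rule for PFS2 and OS yields the promised 0.05 at the final analysis only if exactly 134 PFS2 and 107 OS events have occurred

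*SAP*

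**What the plan says.** SAP 5.1.1 tests ORR, PFS2 and OS in sequence after PFS, "each with an overall two-sided alpha of 0.05". The rule for the last two reads: "alpha spending at the primary analysis time point and the final analysis point will be determined by a linear alpha spending function". The formula follows: "the cumulative alpha to be spent will be the total alpha (0.05) multiplied by the proportion of the observed number of the events", relative to a planned count. The denominators are given at the end of the section: "A total of 134 PFS2 events and a total 107 OS events are expected at the final analysis". No maximum is stated, and nothing says that the final look receives the unspent remainder.

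Three further statements limit where the rule applies:
- An endpoint already rejected is closed: "it will remain being rejected and will not be re-tested at the next analysis timepoint".
- ORR has one chance: "The ORR will only be tested at the primary analysis time point".
- The SAP calls the PFS2 count targeted in its worked example: "if 59% targeted PFS2 events are observed at the primary analysis".

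On timing, Protocol 3.1 lists three data cutoffs and says of the last: "A third will occur at the end of the study". Protocol 3.1 and 17.9.1 put the end of study at roughly 8 years after first randomization or at the sponsor's decision. Protocol 3.1 and 11.2 describe 134 and 107 as approximate counts expected by then, with 81 and 64 expected at the primary PFS analysis. The SAP does not define its final analysis point; its link to the end-of-study cutoff rests on these matching counts. The Amendment 6/EEA-1 summary states that the primary analysis has been completed and the study unblinded.

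**The concern.** A spending function indexed to a planned maximum works at an interim look. At the last look the usual convention is to bring cumulative alpha to its full value, whatever the event count, and to solve the boundary from the actual information fraction. The SAP instead applies the interim formula again at the end.

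The final cutoff is not event-driven. The sponsor-decision clause would allow a stop at the targeted counts, but nothing requires it. One cutoff also serves both endpoints, so it matches both denominators only if the two counts happen to coincide.

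PFS2 and OS are the second and third secondary endpoints in the confirmatory hierarchy. As written, their final critical values depend on how far the counts at a partly discretionary cutoff, chosen after unblinding, fall from a planning projection.

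**Working it through.** **Plan's own figure.** 0.05 × 0.59 = 0.0295, as in the SAP example. At the projected first look: PFS2 0.05 × 81/134 = 0.0302; OS 0.05 × 64/107 = 0.0299.

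**Inputs.** Overall two-sided alpha 0.05 and denominators 134 and 107 (SAP 5.1.1). First-look counts 81 and 64, PFS2 HR 0.75 (medians 72 and 96 months), OS HR 0.80 (medians 100 and 125 months) (Protocol 3.1, 11.2). N = 360 randomized 1:1, 24-month accrual (Protocol 11.2).

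**Method.** With d1 events at the first look and d2 at the final, the two log-rank Z statistics are bivariate normal with correlation √(d1/d2).
- First-look two-sided level: 0.05 × d1/expected.
- The final bound is solved so that the null rejection probability over both looks equals 0.05 × d2/expected (as written) or 0.05 (full spend).
- Power is the probability of rejection at either look, with drift |ln HR| × √d / 2 and each endpoint taken on its own.

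| Endpoint, d1 → d2 | Cumulative alpha as written | Final nominal level: as written / full spend | Power: as written / full spend |
|---|---|---|---|
| PFS2 81 → 134 | 0.0500 | 0.0314 / 0.0314 | no difference |
| OS 64 → 107 | 0.0500 | 0.0315 / 0.0315 | no difference |
| PFS2 81 → 124 | 0.05 × 124/134 = 0.0463 | 0.0280 / 0.0329 | 31.7% / 33.4% |
| OS 64 → 98 | 0.05 × 98/107 = 0.0458 | 0.0277 / 0.0332 | 17.0% / 18.3% |
| PFS2 81 → 107 | 0.0399 | 0.0226 / 0.0368 | 26% / 30% |
| OS 64 → 86 | 0.0402 | 0.0229 / 0.0366 | 14% / 17% |
| PFS2 81 → 142 | 0.05 × 142/134 = 0.0530 | 0.0341 / 0.0304 | – |
| OS 64 → 114 | 0.05 × 114/107 = 0.0533 | 0.0345 / 0.0304 | – |
| PFS2 89 → 163 | 0.0608 | 0.0402 / 0.0266 | – |
| OS 68 → 131 | 0.0612 | 0.0412 / 0.0274 | – |

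**Linking counts to dates.** The plan gives no loss rate, so one is assumed. With monthly event hazard λ = ln 2/median, loss hazard η, s = λ + η and uniform accrual over 24 months, expected events per arm at month T (T > 24) are

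180 × (λ/s) × [1 − (e^(−s(T−24)) − e^(−sT)) / (24s)].

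At 10% loss per year (η = −ln 0.9/12):

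| Month | PFS2 events | OS events | Cumulative alpha, PFS2 / OS |
|---|---|---|---|
| 84 | 124.3 | 98.4 | about 0.046 for both |
| 93 | 131.6 | 104.8 | 0.0491 / 0.0490 |
| 96 | 133.8 | 106.7 | about 0.050 for both |
| 99 | 135.9 | 108.6 | 0.0507 / 0.0507 |
| 108 | 141.6 | 113.7 | about 0.053 for both |

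In this model the 80% counts (107 PFS2, 86 OS) are reached at months 67.0 and 69.5, more than two years before year 8.

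**Sensitivity to the loss rate.** The 10% rate gives 80.5 PFS2 and 61.9 OS events at month 48 (plan: 81 and 64) but only 151 PFS events (plan: 165). A rate of 3.5% per year gives 165 PFS events at month 48 but 162.9 PFS2 and 130.8 OS events at month 96, which is the source of the 163 and 131 rows. No single common rate fits both projections, so the two are shown as a range.

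**One cutoff, two denominators.** With PFS2 as planned and death hazards 10% lower, month 96 gives 133.8 PFS2 events but 98.1 OS events. PFS2 is then on target while OS cumulative alpha is 0.0458.

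**The case against.** The strongest reply is that the overrun is not a real risk. The same section calls 0.05 the total, promises it as the overall level and claims strong control, so a reader would infer a cap. That stands as to intent: the overrun is a missing cap that conflicts with the SAP's own statement, not a planned inflation.

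Second, a shortfall is conservative and breaks no stated guarantee on type I error. That is true. But the loss buys nothing, because no later analysis can use the withheld alpha, and an inferred cap does not help.

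Third, the effect is small, and the loss rates behind the dates are assumptions that do not fit the whole plan. Both points stand. Endpoint-specific censoring, such as the PFS2 rules in SAP 5.3.5, is not modelled and could explain the misfit. The dates are illustrative; the alpha and nominal levels for given counts do not depend on the loss rate. The actual first-look counts are not in the documents.

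Fourth, an amendment after unblinding that raises a nominal level has its own credibility cost, and keeping the conservative rule is defensible. This bears on how the fix is documented. A cap alone would settle the overrun but leave the shortfall.

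**Conclusion.** The rule is wrong as written, and the point is minor. The formula meets its own 0.05 only at exactly 134 and 107 events, while the cutoff is not tied to those counts.

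- Near year 8 the departure is negligible (0.049 to 0.051 at 10% loss per year).
- A year early: cumulative alpha 0.046, final nominal level 0.028 instead of 0.033, and a power loss of 1.7 points for PFS2 and 1.3 for OS.
- At 80% of the counts: cumulative alpha 0.040 and a loss of about 3 to 4 points.
- Overruns, read literally: 0.053 a year late, and about 0.061 at year 8 if loss were 3.5% per year.

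These figures assume exponential times with the protocol's medians, one common loss rate, and first-look counts equal to the projections (81 and 64) except in the 3.5% case, where the model's own 89 and 68 are used. Powers are stand-alone; inside the hierarchy they are lower, because the endpoints ahead must be rejected first. The point matters only for an endpoint still open after the primary analysis. If ORR failed at its single test, the natural reading is that neither PFS2 nor OS is tested at all.

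**What to change.** Before the final data cutoff, amend SAP 5.1.1 for each of PFS2 and OS still open:
- The first look keeps the alpha already spent, 0.05 × min(1, observed/planned events).
- The final analysis brings cumulative two-sided alpha to exactly 0.05, whatever the event count.
- The final critical value is computed from the actual ratio of primary-analysis to final-analysis events.

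Date the amendment, and record that neither it nor the final cutoff date was chosen from the first-look PFS2 or OS results. If the count falls short, make the amended boundary the confirmatory one and report the as-written boundary beside it.

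The cost is one or two sentences, with no burden on patients or data. It is not wholly free: the change follows unblinding and, in a shortfall, raises the final nominal level (for example from 0.028 to 0.033 at 124 PFS2 events), which is why its independence from the first-look results must be on record.

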## 5.1.2. Data Handling Rules

There is no imputation planned for missing efficacy endpoint values.

## 5.2. Primary Efficacy Endpoint(s)

### 5.2.1. Definition

The primary endpoint of this study is PFS as assessed by the independent review committee (IRC), defined as the duration from the date of randomization to either progression to multiple myeloma, according to the IMWG diagnostic criteria for MM, or death due to any cause, whichever occurs first. Progression evaluations for the primary endpoint/final analysis were based on IRC review, in a blinded fashion, to objectively and consistently implement the IMWG diagnostic criteria for MM. Data from the central laboratory, local clonal plasma cell assessment and images performed at the study site (or designated facility) assessed by independent radiological review were provided to IRC for progressive disease identification. Subjects who start anti-cancer therapies for multiple myeloma without disease progression will be censored at the last disease assessment before the start of subsequent therapies. Subjects who withdraw consent from the study before disease progression will be censored at the last disease assessment before withdrawal of consent to study. Subjects who are lost to follow-up will be censored at the last disease assessment before the subjects were lost to follow-up. Subjects who have not progressed and are still alive at the clinical cut-off date for analysis will be censored at the last disease assessment. Subjects without any post-baseline disease assessment will be censored at randomization.

Determination of dates of PFS event and dates for censoring is summarized in [Table 4](#) as follows.

